**Treatment technique:**

For the Pec infiltration, the patient will be in the supine position. The pectoralis major and pectoralis minor muscle layers will be identified via ultrasound. Using sterile technique, a nerve block needle will be inserted and advanced under ultrasound guidance until it is below the fascial covering of the pec minor muscle layer. Gentle aspiration for air or blood will be performed in 5cc incremental doses. Then injection of 10 mL of bupivacaine 0.25% with epinephrine 1:200,000 and 10mL of a mixture of liposomal bupivacaine and saline (5 mL liposomal bupivacaine and 5 mL saline) for a total injection for pec 1 block of 20 mL. For each 5cc of local anesthetic injected, aspiration will be performed. Upon completion of the injection the needle will be removed. We will then use the ultrasound probe to identify the second rib on anterolateral chest wall and

move the probe to the 4th rib. Here we will identify the pec minor and serratus anterior muscles. We will advance our needle under ultrasound-guidance beneath pec minor and above serratus anterior or if unable to visualize the serratus/pec minor border will inject under the serratus anterior. Here we will inject 10 mL 0.25% bupivacaine with epinephrine 1:200,000 followed by 20 mL mixture of 15 mL liposomal bupivacaine and 5 mL saline for a total volume of 30mL for Pec 2 Block. Upon completion of the injection, the needle will then be removed and the patient will be monitored in the preoperative area until he/she is brought into the operating room for their procedure.

If deemed necessary for coverage the surgeon will be allowed to inject additional local anesthetic up to a maximum of 40 mL of 0.25% bupivacaine. This will be noted in the chart.

For the surgeon infiltration, the patient will be brought directly to the operating room where intraoperative anesthetic with an opioid-sparing MAC technique will be provided as described below. Just prior to the skin incision, 0.25% bupivacaine will be used to infiltrate the dermis and subcutaneous space in the proposed incision. Throughout the procedure, additional incisional bupivacaine infiltration into the surrounding tissues will be performed as needed for local anesthesia. A total of up to 30 mL of 0.25% bupivacaine will be divided equally for the two sides of the incision. An additional 5 mL of 0.25% bupivacaine will be infiltrated into the pectoralis major muscle at the deep margin of resection. Accidental intravascular injection is minimized by continuous needle movement and frequent aspiration.

The following vital signs will be monitored throughout the procedure: Heart rate, blood pressure, oxygen saturation, and respirations, and patient's state of consciousness. We will monitor the patient until they are brought to the operating room for surgery.

All patients will receive multimodal analgesia in the preoperative area. They will receive 975 mg of oral acetaminophen and 300 mg of gabapentin orally prior to surgery. The intraoperative anesthetic will be an opioid-sparing MAC anesthetic. If patients are unable to tolerate procedure under MAC they would be converted to a general anesthetic with an laryngeal mask airway (LMA). For those patients receiving a lumpectomy with axillary dissection, they will receive a general anesthetic with LMA. Patients will receive IV midazolam 0-2 mg followed by 40-100mg of IV lidocaine, and followed by a propofol infusion and a 0.25 mg/kg bolus of ketamine followed by 0.25 mg/kg /hour infusion of ketamine. Opioids will be avoided unless HR or BP increases by 20 % above baseline. Then only short acting opioids (fentanyl) will be given.

In the recovery room if the patient experiences pain greater than 5/10 they will receive either IV or oral pain medications. If pain score is less than 5 patients will get non opioid medications unless the patient desires an opioid medication.

When the operation is complete the patient will either be brought to the PACU or Phase II. Each day a member of the research team will contact and evaluate the patient for signs of complications and ask the patient their minimum and maximum pain score

(scores will be evaluated at 1 hr, 2 hr, 6hrs, 24hrs, 48hrs, 72hrs). They will record daily opioid use, any modality related complications, how many phone calls were made regarding pain control and modality related complications. At time period 72 hours a Quality of recovery survey (see appendix) and OBAS (see appendix) survey will be presented to patient. Patients will be offered phone calls for contact, but patients may opt to be contacted via text message if they do not wish to have phones calls. We will provide patients with an additional consent for text messaging if they wish to use this method.

At 3 months, 6 months, and 12 months patients will be called to answer a survey with regards to chronic pain.

Patients will be instructed to take acetaminophen 1000 mg every 8 hours while at home for 3 days. They will be given a prescription of opioid pain medications either oxycodone or hydromorphone and will be instructed to take as needed for pain.

### **Enrollment procedures:**

Patients will be recruited from the group of adult surgical patients at the University of Minnesota undergoing partial mastectomy procedures. Patients will be approached in either the surgeon's clinic or pre-assessment clinic by a research staff member to determine their interest in participation. Subjects interested in the study will be presented with consent and Health and Insurance Portability and Accountability Act (HIPAA) forms, with the REDCap e-consent process being preferentially used. The patient will review the forms with the surgeon, anesthesiologist or other study staff. Subjects will be reminded that participation is completely voluntary, and that they may stop participation at any time without question or penalty. The surgeon or anesthesiologist will answer any questions that the subjects may have about the study. If the patient decides to participate, they will be asked to sign the consent and HIPAA forms. One copy will be saved for study records, and the subject will be provided with a copy of the forms for their own records. If they need additional time to consider enrollment, they will be asked if we can reach out to them by phone the night before surgery or if we should revisit the study with them on the day of surgery. If the patient is unable to be consented prior to day of surgery, the research staff will approach them in the preoperative surgical area. These patients will have significant time to review the study with research staff as well as the physicians performing the procedure due to the fact they arrive several hours prior to their scheduled surgery. All subjects will have enough time to ask questions about the study and the potential risks involved regardless of which venue they are consented. Any patient that refuses to participate in the study at any time point will be placed on a secured list to avoid duplicate attempts to recruit them. All forms will be locked and stored in a file cabinet in the research department. Enrolling consecutive patients will help reduce selection bias. Any patient who does not complete all necessary paperwork and answer questions at the appropriate time intervals will be eliminated from the study. Patients lost to follow-up, or patients who decide not to participate in the study after initial enrollment, or patients who are eliminated from the study for any reason will have their study records shredded and will not be included in the final data-analysis.

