**Randomization procedure:**

Patients will be identified by members of the treatment team in either the surgeon's clinic, pre-assessment clinic, or preoperative area. Patients who have opted out of research will not be asked to participate in the study. Patients will be approached to consent for the study by a surgeon, anesthesiologist, or member of the research team. Patients who agree to participate in the study will sign both a study consent and HIPAA authorization allowing the use of specified information contained in medical records for research purposes.

A random number generator will be used to determine if the patient will have pectoralis liposomal bupivacaine infiltration or bupivacaine infiltration directly into the incision space. The primary or co-investigator will access the number generator in the pre-op area. The website [www.random.org](http://www.random.org) will be used as the random number generator.

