### **Assessments:**

Post-operatively patients will be evaluated 1 and 2 hr post-operatively by the PACU nurse and 6 hrs post-operatively by a medical student or research coordinator. This person will not be aware of the patient's mode of analgesia. The medical student or research coordinator will evaluate at, 24, 48, and 72 hours post injection +/- 5 hours. If sent home they will be contacted via preferred contact method at, 24, 48, and 72 hours post-operatively. Patients will be asked to rate their pain on scale of 0-10. The amount of opioids used by the patient will be recorded as will any other adjuvant pain medication used. Any modality related complications will be recorded. The patients will be asked at 72 hours post-injection to fill out a quality of recovery and OBAS survey. All complications will be recorded from time of consent to last follow up date. Patients will be called at 3, 6, and 12 months post operatively to fill out a chronic pain survey.

All data will be recorded in a locked encrypted database. Data collection will continue until Postoperative day ( POD ) #3. Should patients be re-admitted to the hospital in the next two weeks (Up to POD #19) for pain a notation will be made in study records. Additional contacts by the research assistant or medical student will continue up until the 3, 6, and 12 month postoperative times.

An analysis of the total cost of analgesics (including patient costs for opioid prescriptions) will be tabulated at the conclusion of the study to determine the most cost effective treatment option as this will be added into the cost of hospitalization including the number of days each patient spent in the hospital.

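### The plan deletes randomised patients with incomplete follow-up from the analysis and shreds their records, which can bias the primary opioid comparison

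*Combined protocol and SAP*

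**What the plan says.** Two sentences at the end of Enrollment procedures set the rule. The first defines who is removed: "Any patient who does not complete all necessary paperwork and answer questions at the appropriate time intervals will be eliminated from the study". The second adds patients who are lost or withdraw after enrolment, and gives the consequence: "patients who are eliminated from the study for any reason will have their study records shredded and will not be included" in the final analysis.

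Randomization procedure fixes when allocation happens: "The primary or co-investigator will access the number generator in the pre-op area". Every timed question comes later. Assessments lists 1, 2 and 6 hours, and then "The medical student or research coordinator will evaluate at, 24, 48, and 72 hours post injection +/- 5 hours". Treatment technique adds the long-term contacts: "At 3 months, 6 months, and 12 months patients will be called to answer a survey with regards to chronic pain".

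Statistical Considerations names total opioid use as the primary outcome and gives 112 patients (56 per group), 80% power, a 35% decrease and alpha 0.05. Outcome Measurements names ANOVA and chi-squared techniques. Neither section defines an analysis population, a missing-data method, a sensitivity analysis or an attrition allowance.

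Some passages limit the damage. Under Assessments, "All data will be recorded in a locked encrypted database", and nothing says that database entries are erased. Project Medications keeps hospital doses in the medication record in the chart. Follow-up is made easier because "patients may opt to be contacted via text message", and Data collection has coordinators check that follow-up is complete.

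**The concern.** This is a written completers-only rule, not a gap that ordinary practice would fill. Loss to follow-up and missed timed questions can only occur after the draw. The one group outside this is patients who consent and then withdraw before allocation.

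Removing randomised patients because of what happens after treatment gives up the comparability that randomisation provides. Pain and opioid use could plausibly affect whether a patient answers on time, and could do so differently by arm: one arm has an ultrasound-guided block before surgery, the other goes straight to the operating room, and only the assessors are described as blinded.

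Home opioid use is the most exposed part of the primary outcome. It is reported by patients at the contacts, and no source independent of the patient is named. An ordinary completers analysis can be redone later; destroyed records may not allow that.

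The reach of the rule is also unclear, because neither the required paperwork nor the required times are defined. Read literally, a patient with full 72-hour data is deleted for missing a 12-month call. Yet Assessments says "Data collection will continue until Postoperative day ( POD ) #3" and treats later calls as additional. A related item under Exclusion criteria (overnight intubation, or inability to report pain straight after surgery) can also be known only after treatment.

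**Working it through.** **Inputs from the plan.** 56 per arm, 80% power, 35% decrease, alpha 0.05 (Statistical Considerations); contacts at 24, 48 and 72 hours and at 3, 6 and 12 months (Assessments).

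**Assumptions.** The plan gives no SD, control mean, sidedness or loss rate. I take a two-sided two-sample t-test with equal SDs and scale the control mean to 1. All loss rates below are illustrative.

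**The plan's own figure.** Without an SD, 56 per arm cannot be reproduced, only inverted. Power of 80% at 56 per arm needs a standardised difference d = 0.534, so the implied coefficient of variation is CV = 0.35 / 0.534 = 0.655. The normal approximation gives d = 0.529 and CV 0.66.

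**Bias with no true effect.** Let each patient's chance of deletion be r × (own use / mean use), where r is the arm's deletion rate. The mean among retained patients is then

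1 − r × CV² / (1 − r), with CV² = 0.655² = 0.429.

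- r = 3%: 0.987; 5%: 0.977; 6%: 0.973; 10%: 0.952; 20%: 0.893.
- 3% v 6%: 1 − 0.9726/0.9867 = 1.4%.
- 5% v 10%: 1 − 0.9523/0.9774 = 2.6%.
- 10% v 20%: 1 − 0.8927/0.9523 = 6.3%.

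Simulation with gamma-distributed use and a pooled t-test (200,000 runs per cell, 56 per arm before deletion) agrees:

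| Deleted, arm v arm | False difference, CV 0.655 | Type I error | False difference, CV 0.5 to 0.8 | Type I error |
|---|---|---|---|---|
| 3% v 6% | 1.4% | 5.1% | 0.8 to 2.1% | 5.0 to 5.1% |
| 5% v 10% | 2.6% | 5.3% | 1.5 to 3.9% | 5.1 to 5.5% |
| 10% v 20% | 6.2% | 7.3% | 3.6 to 9.4% | 6.3 to 8.7% |
| 10% v 10% | 0% | 5.0% | 0% | 4.9 to 5.0% |

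**Stronger selection.** Suppose instead that deleted patients average k SDs above their arm mean. The retained mean is [1 − a(1 + k × CV)] / (1 − a) for deletion rate a. With CV 0.66 and k = 1, 5% v 15% gives 0.965 and 0.883, a false difference of 8.5% with type I error about 9.5%. The extreme case of 5% v 25% gives 19.2% and 27.5%. Swapping the arms reverses the sign. Equal loss is not always safe: 10% deleted in each arm, high users from one and low users from the other, each by 0.5 SD, gives type I error of about 8.6%.

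**Power.** With d = 0.534 and 56 × (1 − loss) per arm:

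| Deleted | Per arm | Power |
|---|---|---|
| 5% | 53.2 | 0.779 |
| 10% | 50.4 | 0.757 |
| 20% | 44.8 | 0.705 |
| 30% | 39.2 | 0.646 |

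If 56 already contains an unstated allowance and only 50 per arm are needed (d = 0.566), power is 0.803, 0.755 and 0.696 at 10%, 20% and 30% deleted.

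**Reach of the rule.** If 3% miss each contact and it is always the same patients, 3% are deleted. If misses are independent, counting only 24, 48 and 72 hours gives 1 − 0.97³ = 0.087, and counting the 3-, 6- and 12-month calls too gives 1 − 0.97⁶ = 0.167. At 1% per contact the figures are 1 − 0.99³ = 0.030 and 1 − 0.99⁶ = 0.059.

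**The case against.** The strongest reply is that nothing in the documents shows losses will differ by arm. The follow-up assessors are blinded, both arms share one post-operative protocol, and text messages, a 5-hour window and coordinator checks should keep losses low. With small losses the bias is close to nil, and with equal losses of similar patients it is zero. This stands as a limit on size. It does not change the rule, which would apply to whatever losses occur.

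Second, data may survive. Shredding suggests paper, database erasure is not stated, hospital doses stay in the chart, and Data collection also records daily opioid totals and leftover opioids at 72 hours. This stands in part: irrecoverable loss is not established, and the 72-hour items could fill a missed 24- or 48-hour contact. They still come from the patient, so they do not help for someone lost before 72 hours, and surviving data would still be left out of the analysis.

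Third, the primary outcome has no stated time window, so 72 hours is an inference from the data-collection schedule. That is correct and is treated here as an assumption.

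Fourth, deletion for a missed late call is not the natural reading. I agree that it is the literal reading rather than the likely intent. The 17% figure depends on it and on independent misses.

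Fifth, adverse events reach the chart, the safety board and the IRB by other routes, and the rule mentions only the final analysis. So what is kept after a discontinuation for a serious adverse event is a point to clarify, not an established loss of safety data.

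**Conclusion.** The concern holds, and the rule must be changed. As written, it removes randomised patients for post-randomisation reasons, and nothing in the statistical sections overrides it. That conclusion rests on the text alone.

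The harm to the primary result is possible rather than shown. It needs losses that differ between arms in rate or reason and that relate to opioid use. Under the proportional-deletion model the effect runs from near zero to modest; strong selection with very unequal loss would make it larger. Direction cannot be predicted. The power cost depends on whether 112 already includes an allowance, which the plan does not say. A larger sample would restore power but would not remove the bias.

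The case for changing the rule now is that its effect cannot be known in advance and may not be repairable afterwards.

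**What to change.** Replace the last two sentences of Enrollment procedures with text stating that:

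1. All randomised patients are analysed in their assigned arm, using all data collected up to withdrawal, subject to any revoked authorisation. Patients who leave between consent and the draw are counted in the participant flow only.
2. A missed later survey removes the patient from that survey's analysis only.
3. Paper and database study records of randomised patients are kept, and adverse events of treated patients stay in the safety counts and stopping proportions.

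In the statistical sections:

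- Pre-state a method for missing 24-, 48- and 72-hour opioid data, for example multiple imputation informed by the recorded 72-hour items, with a sensitivity analysis.
- Report losses by arm and reason.
- State that 80% power assumes all 112 contribute primary-outcome data, unless an allowance is already included.
- Say that the post-operative item under Exclusion criteria is not used to remove randomised patients from the analysis.

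As a clarification, reconcile Enrollment procedures, Assessments and Stopping Criteria on what is recorded and kept for patients discontinued after a serious adverse event.

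The cost is protocol wording and a little more analysis, with no extra patients or visits. Compared with the deletion rule, the analysable number rises. The consent pages were not available to this review, so check the new wording against their withdrawal terms; a consent revision, if one proves necessary, would be an added cost.

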### **Assessments:**

Post-operatively patients will be evaluated 1 and 2 hr post-operatively by the PACU nurse and 6 hrs post-operatively by a medical student or research coordinator. This person will not be aware of the patient's mode of analgesia. The medical student or research coordinator will evaluate at, 24, 48, and 72 hours post injection +/- 5 hours. If sent home they will be contacted via preferred contact method at, 24, 48, and 72 hours post-operatively. Patients will be asked to rate their pain on scale of 0-10. The amount of opioids used by the patient will be recorded as will any other adjuvant pain medication used. Any modality related complications will be recorded. The patients will be asked at 72 hours post-injection to fill out a quality of recovery and OBAS survey. All complications will be recorded from time of consent to last follow up date. Patients will be called at 3, 6, and 12 months post operatively to fill out a chronic pain survey.

All data will be recorded in a locked encrypted database. Data collection will continue until Postoperative day ( POD ) #3. Should patients be re-admitted to the hospital in the next two weeks (Up to POD #19) for pain a notation will be made in study records. Additional contacts by the research assistant or medical student will continue up until the 3, 6, and 12 month postoperative times.

An analysis of the total cost of analgesics (including patient costs for opioid prescriptions) will be tabulated at the conclusion of the study to determine the most cost effective treatment option as this will be added into the cost of hospitalization including the number of days each patient spent in the hospital.

### **Blinding Procedure:**

The research coordinator in this study will be blinded to the method of analgesia for the patient. The research coordinator will assess pain one time per day. This person will not be responsible for any clinical testing and will record all data in the protected database daily. Any questions from the patient will be referred to the on-call resident or staff on call.

### **Subject Identification:**

Subject names will be collected as part of the informed consent process, and are thus considered private data. At the time of consent, subjects will be assigned an independent study identification (ID) number that will be used subsequently throughout the study. All data sheets will be identified only by an ID number. Data will be stored in a locked file cabinet in the research office at UMMC. Consent forms will also be stored in a separate locked file cabinet. Web based data will be accessible only by the primary investigator and research staff. It will be password protected and any information that is printed will be stored in a locked file cabinet in the research office at UMMC.

**Risks:**

Risks to subjects of this study include

- Failure of the block
- Wound infections
- Complications related to placement of the Pec block including
  - lung perforation, nerve injury or intravascular injection.
- Local anesthetic toxicity

These complications all fall within the standard risks of surgery. Any intervention being provided as a part of this study falls within the standard of care of Pec infiltration and surgeon infiltration and are within the standard treatments for post-operative pain and are currently used as analgesic options at UMMC. There may also be certain unforeseen risks that will be treated as necessary by the operating physician. All complications will be noted by the operating physician and reported to the IRB and research staff. Appropriate records will be made in the patient chart, and the patient will be treated as needed by the operating physician.

Any unforeseen injuries that may occur to the subjects while enrolled in this study will be treated as needed by the operating physician. No provision has been made for financial payments or other forms of compensation (such as lost wages, medical cost reimbursement, lost time or discomfort) with respect to such injuries. No arrangement has been made for further compensation from UMMC. However, patients do not waive any legal rights by signing a consent form.

